**Figure 1-1 Study Design Overview**

### 3.2 Endpoints and Associated Variables

The following list of study endpoints and associated variables will be used to Investigate the Cardiac Effects and Safety of Paroxetine in Healthy Adult Participants.

#### 3.2.1 Primary Endpoint

- Change in QTc from baseline ( $\Delta$ QTc)

#### 3.2.2 Secondary Endpoint

- Changes in vital signs (blood pressure, heart rate and oral body temperature) from baseline
- Occurrence of adverse events (AEs), serious adverse events (SAEs), hematological and clinical laboratory tests, vital signs, and physical examination

#### 3.2.3 Pharmacokinetic Variables

Pharmacokinetic concentration data will be obtained at time point(s) described in the schedule of assessment in Section 6.1.

Unless otherwise stated, derivation of PK parameters will be the responsibility of CPMS group, Parexel.

The following plasma PK parameters listed in [Table 3-1](#) for paroxetine following repeated dose administration will be determined using non-compartmental analysis.

**Table 3-1 Plasma Pharmacokinetic Parameters after Multiple Dose Administration after Last Dose (on Day 7, 14 and 21)**

Parameter	WNL Name	CDISC Name	Definition
$C_{\max}$	Cmax	CMAX	Maximum observed concentration in a dosing interval after last dose administration
$t_{\max}$	Tmax	TMAX	Time corresponding to occurrence of $C_{\max}$ after last dose administration

### 3.2.4 Safety Variables

- Physical examinations
- Vital signs (Blood Pressure, heart rate and oral body temperature)
- 12-lead electrocardiogram (ECG): Heart rate, PR interval, Q waves, QRS interval, QTcF interval
- Clinical laboratory tests (haematology, clinical chemistry, coagulation, and pregnancy testing, other screening tests.)
- Adverse event (AE)/serious adverse event (SAE) assessments
- Prior and concomitant medication assessments
- Pregnancy test

### 3.2.5 Exploratory Variables

Not Applicable.

## 4 STATISTICAL METHODS

### 4.1 Data Quality Assurance

All tables, figures, and data listings to be included in the report will be independently checked for consistency, integrity, and in accordance with standard Parexel procedures.

### 4.2 General Presentation Considerations

This section is not applicable to PK data.

#### 4.2.1 Treatment

All participants will receive active treatment with paroxetine tablets once daily with titration steps every week over a maximum treatment period of 3 weeks. This is followed by tapering over the subsequent period of 10 days:

- Days 1-7: 20 mg once daily
- Days 8-14: 40 mg once daily
- Days 15-21: 60 mg once daily
- Days 22-26: 40 mg once daily
- Days 27-31: 20 mg once daily. If participants are not able to withdraw from 20 mg once daily directly due to withdrawal effects, an additional tapering dose step of 10 mg once daily may be given for 5 days. Unplanned visits (if needed) will be scheduled for participants who need to visit to clinic due to AEs during home dosing or required to start intermediate tapering dose of 10 mg to be started (for both clinic and home dosing) during the tapering period.
- Day 32 (or 37) onwards: complete stop of paroxetine

#### 4.2.2 Study Day

Study days will be numbered relative to the first day of study drug administration.

- If the date of event is before the study drug administration, then:  
Study day = (Date of event – Date of study drug administration [i.e. Day 1] )
- If the date of event is on or after the study drug administration, then:  
Study day = (Date of event – Date of study drug administration [i.e., Day 1]) + 1
- If the date of event is missing, then study day is also missing.

#### 4.2.3 End of Study

A participant is considered to have completed the study if they have completed all phases of the study, including the last visit for any protocol-related activity (last participant, last visit) as shown in the SoA (Section 6.1) are completed.

The end of the study is defined as the last visit of the last participants in the study.

#### 4.2.4 Baseline

Baseline is defined as the mean of Day -1 timepoints recorded before first dose of study treatment administration for all types of measurements except for primary analysis.

The baseline definition will be used for following safety variable:

- Vital signs
- Clinical laboratory tests

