| Study Visit   | 1          |    | 2               | 2  | 3               |   |   | 4               |    |    | 5               |                 |  | Discontinue / Withdrawal Visit | 6                             |
| Study Day   | -28 to -31 | -2 | -1              | 1  | 6               | 7 | 8 | 13              | 14 | 15 | 20              | 21              | 22                                       | -                              | Up to 14 days after last dose |
| Paroxetine concentrations                        |            |    | X               |  | X               |   |   | X               |    |    | X               |                 |  |                                |                               |
| Haematology with differential                        | X          |    |                 |  |                 |   |   |                 |    |    |                 |                 |  | X                              | X                             |
| Clinical and renal/liver chemistry                   | X          |    |                 |  |                 |   |   |                 |    |    |                 |                 |  | X                              | X                             |
| Pregnancy test, alcohol and drug of abuse tests  | X          |    | X               | X  |                 |   |   | X               |    |    | X               |                 |  | X                              | X                             |
| FSH test   | X          |    |                 |  |                 |   |   |                 |    |    |                 |                 |  |                                |                               |
| COVID-19 test                                        | X          |    | X               | X  |                 |   |   | X               |    |    | X               |                 |  | X                              | X                             |
| Serology (HIV, HBV, and HCV)                                      | X          |    |                 |  |                 |   |   |                 |    |    |                 |                 |  |                                |                               |

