7. For Study Days 1 (Visit 2, 20 mg), Day 8 (Visit 3, 40 mg) and Day 15 (Visit 4, 60 mg), the participant will take the first dose of the next dose level (20, 40 and 60 mg respectively) under supervision of staff, remaining under observation for 3 hours post-dose and will be discharged afterwards.
8. SAEs must be collected from signing of informed consent if considered related to study procedures.
9. Vital sign measurements will include oral body temperature, systolic and diastolic blood pressure (BP), and pulse rate. Triplicate BP measurements will be performed in supine position at Screening only.
10. Vitals, laboratory assessments (coagulation parameters, haematology with differential, clinical and liver chemistry, pregnancy test, and paroxetine concentrations samples) and ECG data will all be captured at visits on site. During the treatment period, all laboratory samples and vitals (including one paroxetine concentration sample) should be obtained pre-dose.
11. All ECGs will be performed in triplicate collected within 5 min at each timepoint. ECG triplicates will be performed once at Screening (Visit 1), and at Follow-Up Visit and at discontinuation or withdrawal visits. At Visits 2 (Day -1), 3 (Day 7), 4 (Day 14), and 5 (Day 21) ECG triplicates will be performed 15 min pre-dose (-0.25 h) and post-dose at the following timepoints 1, 2, 3, 4, 4.5, 5, 5.5, 6, 8, 10, 12h. Each ECG triplicates will be combined with paroxetine concentration assessment. Paroxetine concentrations at Visits 3 (Day 7), 4 (Day 14), and 5 (Day 21) will be procured at the following timepoints: -0.25, 1, 2, 3, 4, 4.5, 5, 5.5, 6, 8, 10, 12 h. One sample will be collected for paroxetine concentrations on Day -1 at 0.25h (pre-dose). The paroxetine dose should be taken at the same clock time each time, at a time approximately between 07:00-010:00 (7to 10 am). When scheduled for the same time, ECGs should be performed before blood sampling to avoid impact on ECG parameters.
12. At Visits 2 (Day -1), 3 (Day 7), 4 (Day 14), and 5 (Day 21), follow-up visit and at discontinuation or withdrawal visits, serial ECG review will be performed by Mortara system

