#### 4.12.3 Clinical Laboratory Evaluation

Clinical laboratory test results of haematology, clinical chemistry, coagulation, pregnancy testing and other screening tests (FSH and oestradiol as needed in WONCBP only, urine alcohol and drug screen, serology) will be provided by subject. A list of current reference ranges of laboratory assessments is included in Section 6.3. Since laboratory ranges can be subject to changes over time the reference ranges presented in Section 6.3 might differ from the ones used and presented on SDTM. For analysis purposes only the ranges present on the SDTM will be used.

All TLFs will display only the standard international (SI) units after conversion by means of standard conversion factors.

Quantitative clinical laboratory variables, ie, haematology, clinical chemistry, and coagulation will be summarized using descriptive statistics (n, mean, SD, minimum, maximum and median) by on/off treatment. Additionally, a within-participant change will be calculated as the post-baseline measurement minus the baseline measurement and summarized in the same way.

Baseline definition will be defined in section [4.2.4](#).

Each laboratory result will be classified as low (L), normal (N), or high (H) at each time point according to the laboratory supplied reference ranges. Tabulations will be presented by treatment (on/off treatment).

Measurements obtained at Screening and EOS will not be included in the shift tables.

Frequency tabulations of qualitative clinical laboratory variables will be presented by treatment (on/off treatment).

All laboratory data will be displayed in listings.

Laboratory abnormalities that are considered clinically significant (CS) are recorded in the database as AEs. Therefore, no tabulation of laboratory values meeting any CS criteria will be presented as all relevant information will be presented in the AE summaries.

Results of pregnancy tests (females only), serology, alcohol and drug of abuse tests will be listed only.

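### The SAP sets the laboratory baseline on Day -1, but the schedule plans no haematology or chemistry sample that day, so laboratory change from baseline has no scheduled data

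*SAP*

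**What the plan says.** SAP 4.2.4 states: "Baseline is defined as the mean of Day -1 timepoints recorded before first dose of study treatment administration". It exempts only the primary analysis and lists two safety variables to which the rule applies, vital signs and clinical laboratory tests. SAP 4.12.3 refers back to that definition and says "a within-participant change will be calculated as the post-baseline measurement minus the baseline measurement", for haematology, chemistry and coagulation. On shift tables it adds: "Measurements obtained at Screening and EOS will not be included in the shift tables".

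The schedule is in protocol Table 2 (section 1.3). The rows "Haematology with differential" and "Clinical and renal/liver chemistry" are marked at Screening, Early Discontinuation and Follow-up, and nowhere else. Coagulation has no row. Footnote 10, attached to both rows, lists "laboratory assessments (coagulation parameters, haematology with differential, clinical and liver chemistry, pregnancy test, and paroxetine concentrations samples" among the data captured on site, and continues: "During the treatment period, all laboratory samples and vitals (including one paroxetine concentration sample) should be obtained pre-dose".

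The secondary estimand (protocol section 3, SAP 2.2) names laboratory change from baseline as a variable, summarised by its mean over all the dose levels.

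**The concern.** A change from baseline needs a baseline value, and the SAP allows only a Day -1 value. If no haematology or chemistry sample is planned that day, the programmed tables are empty. The alternative is that someone substitutes the Screening value at programming, which contradicts SAP 4.2.4 and would be an undocumented choice in an open-label study.

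The shift tables fail for a second reason. Correcting the baseline alone would not repair them, because the values a completer does have are excluded by name.

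At stake is one descriptive component of the secondary estimand. The QTc conclusion is not involved.

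**Working it through.** **Step 1: read the grid.** Protocol Table 2 has 15 day columns: Screening (Day -28 to -31), -2, -1, 1, 6, 7, 8, 13, 14, 15, 20, 21, 22, Early Discontinuation and Follow-up.

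| Row | Columns marked | Count | Day -1 |
|---|---|---|---|
| Vital signs | all except -2 and 22 | 15 - 2 = 13 | yes |
| Haematology | Screening, Early Discontinuation, Follow-up | 3 | no |
| Chemistry | same three | 3 | no |
| Pregnancy, alcohol and drug tests | Screening, -1, 1, 13, 20, Early Discontinuation, Follow-up | 7 | yes |
| COVID-19 test | same seven | 7 | yes |
| Coagulation | no row | - | - |

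The row "Pregnancy test, alcohol and drug of abuse tests" is marked on Day -1, but SAP 4.12.3 only lists those results. Neither it nor the COVID-19 test gives a quantitative baseline.

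**Step 2: is this an artefact of the table?** Each row has 15 cells against 15 headers, and other rows do carry a mark on Day -1. Exact days within a visit are less secure: the ECG and paroxetine rows are marked on Days 6, 13 and 20, while footnote 11 places those assessments on Days 7, 14 and 21. A one-column displacement would still not matter, because Screening lies two columns from Day -1. The schedule in SAP 6.1 is damaged in the text available; it is consistent with this reading but is not counted as proof.

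**Step 3: scheduled baselines under SAP 4.2.4.** Scheduled Day -1 haematology or chemistry values per participant: 0. For 36 participants, 0 x 36 = 0; for 40, 0 x 40 = 0. No change can be formed from scheduled data.

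**Step 4: shift tables under SAP 4.12.3.** A completer has 2 scheduled haematology and chemistry values, Screening and Follow-up. Table 2 labels the last column as both follow-up and end of study, so both are excluded: 2 - 2 = 0.

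**Step 5: look for a rescue elsewhere.**
- SAP 4.2.5 admits an unscheduled result that qualifies as baseline. It would still have to fall on Day -1, and none is planned.
- The repeat in protocol 5.4 applies only when a Screening value is out of range.
- Protocol section 8 allows routine results obtained before consent to serve as baseline. Consent is at Screening, so these are not Day -1 values.
- Footnote 10 sets sampling relative to dose but adds no Day -1 haematology or chemistry sample.
- Protocol 9.3.2.1 defines baseline for QTc only, and SAP 4.17 logs only the change to the Enrolled set.

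**Step 6: what a last-value-before-dose rule would give.** One baseline and one post-baseline value make 1 pair per completer, so 36 to 40 pairs if everyone enrolled completes. With Screening as that value:
- Age of baseline at first dose: 28 to 31 days (Table 1; day numbering of SAP 4.2.2).
- Follow-up: last dose on Day 31, plus 9 to 14 days (Table 1), gives Days 40 to 45, which is 39 to 44 days after Day 1.
- Span from Screening to Follow-up: 28 + 39 = 67 days to 31 + 44 = 75 days.

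These figures leave out the optional 10 mg taper step. The lower end relies on the 9-day minimum in Table 1; Table 2 gives only the 14-day maximum.

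**The case against.** The strongest reply is that the grid, not the SAP, may be at fault. Footnote 10 names coagulation, haematology and chemistry and speaks of pre-dose laboratory samples during treatment. SAP 4.12.3 summarises by on and off treatment and leaves Screening and end of study out of the shift tables. Together these make most sense if samples near Day 1 and during treatment were intended. On that view the schedule should be settled first, and the shift-table exclusion might be a legitimate choice. The reply adds that a Screening-to-Follow-up change does not deliver the estimand's mean change over the dose levels, because completers have no scheduled on-treatment laboratory value under any baseline.

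Much of this stands. The documents do not show which text reflects the intention, and the footnote and grid must be reconciled. No baseline rule can create on-treatment data. The contradiction remains, however: the footnote supplies no Day -1 haematology or chemistry sample, and a baseline defined as the last value before dosing works whichever way the footnote is resolved.

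A second reply concerns weight. The endpoint lists (protocol section 3, SAP 3.2.2) attach change from baseline to vital signs and place laboratory tests under occurrence. Protocol 9.3.3 and 9.3.3.1 plan change for vital signs and ECG, not laboratory tests. Clinically significant laboratory findings are reported as adverse events. An empty baseline would probably be noticed at programming. These points limit the importance, but both estimand descriptions and SAP 4.12.3 do call for laboratory change.

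**Conclusion.** The concern holds. As written, the rule produces an empty result: 0 of 36 to 40 participants have a scheduled laboratory baseline, and 0 of a completer's 2 scheduled haematology and chemistry values remain for the shift tables. Coagulation is to be analysed but has no row in the schedule.

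This should be corrected, but it does not threaten the trial's main conclusion. Observed values, low/normal/high classes, listings, laboratory adverse events, vital signs and the QTc analysis are unaffected.

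The conclusion rests on two readings: that the protocol grid is the operative schedule, and that end of study in SAP 4.12.3 means the last column of Table 2. It makes no claim about unscheduled samples or about the laboratory manual, which is not among the documents.

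**What to change.** - **SAP 4.2.4:** keep the Day -1 mean for vital signs. For laboratory tests, define baseline as the last non-missing value before first dose. Under the present grid that is Screening, or the protocol 5.4 repeat where one was taken.
- **SAP 4.12.3:** delete the exclusion of Screening and end-of-study values from the shift tables. Tabulate change and shift from the new baseline to Follow-up, labelled post-treatment, and to Early Discontinuation, labelled on or off drug from the last dose date. The label is needed because protocol 6.6 allows either a taper or an immediate stop.
- **Log:** record the change in SAP 4.17 or, after finalisation, in the Statistical Method Modification Form.
- **Schedule:** reconcile footnote 10, including coagulation, with the grid in both documents. If the grid stands, state that scheduled laboratory change in completers describes the post-treatment state and not change on treatment.

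The cost is wording in two SAP sections, a log entry and small edits to table shells. The drawback is a baseline about four weeks before first dose. If footnote 10 is resolved in favour of treatment-period samples, the schedule grid would also need amending.

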#### 4.2.5 Controlled, Repeat, Retest, Scheduled and Unscheduled Assessment

Repeat, retest, and unscheduled assessment will not be considered for the calculation of summary statistics and figures, unless assessment qualifies as baseline.

Average of controlled and planned (scheduled) assessment will be considered for the calculation of summary statistics and figures, if more than one controlled/planned assessment will be performed at a specific time point.

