### 8.3.3. Electrocardiograms

Standard 12-lead ECG will be obtained as outlined in the SoA (Table 2) using an ECG machine that automatically calculates the heart rate. All ECGs in this study should all be recorded using the same make of ECG device (Mortara Surveyor Telemetry Central and Mortara telemetry transmitters Model: Surveyor S4), with the exception of Screening visit, where CardioSoft® will be used. The Mortara system is validated every 12 months. Monitors will also be available to spot check the calibration when on-site. The readings generated by Mortara surveyor S4 machine will be validated by the cardiologist with their interpretation on whether the findings are significant and related to paroxetine. ECGs must be recorded after 10 minutes rest in the supine position to ensure a stable Baseline. ECGs will be performed and recorded in the eCRF at the times shown in Table 2. The preferred sequence of cardiovascular data collection during study visits is ECG collection first, followed by vital signs, blood sampling, and any remaining assessments for that visit.

At Screening, participants will be excluded based on ECG measurements if the resting QTc is >450msec (mean of three twelve-lead ECG measurements and using Fridericia's correction). The Fridericia QT correction formula (QTcF) must be used for clinical decisions, e.g., at Screening to assess eligibility. Further, all ECGs will be performed in triplicate collected within 5 min, at least 1 minute in between, at each timepoint.

- Triplicate ECGs will be performed at each timepoint as detailed in SOA (Table 2). The mean QTc value will be calculated from the triplicate ECGs for each participant.

- The ECG extractions will be paired with paroxetine concentration samples but will be obtained before the actual paroxetine concentration sampling time to avoid changes in autonomic tone associated with the psychological aspects of blood collection as well as the reduction in blood volume subsequent to blood collection.
- At visits where an ECG is not scheduled, an ECG can be performed if medically indicated.
- All ECG traces will be measured by a third-party vendor, which includes review by a licensed cardiologist. The cardiologist will review the ECGs and provide interpretation on whether the findings are normal, abnormal but non-clinically significant (unrelated to Paroxetine), or abnormal but clinically significant (related to paroxetine).

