### 8.3.6. Study stopping rules, Safety monitoring committee

#### 8.3.6.1. Study Stopping Rules

Participant safety will be continuously monitored by the Sponsor's Medical Monitor, and designated Safety Lead (or delegate) throughout the study. Pertinent findings and conclusions are shared with the product's safety review team for review of the overall benefit-risk profile of the product.

Dependent on regional guidance, any restart following a temporary hold due to stopping rules being met will require prior submission and approval of a substantial Clinical Trial Application (CTA) amendment to the competent authorities.

Dosing will be placed on temporary hold and must be stopped based on full review of all available safety data and discussion with the Investigator if any of the following occur:

- Two or more participants experiencing any Serious Adverse Reaction (SAR) (i.e. a SAE suspected to be at least possibly related to the study treatment(s)

- Two or more participants experiencing an AE which was assessed as severe in intensity (Grade 3) and is considered as potentially related to the study treatment(s).
- One or more participants in the cohort experiencing QTcF interval >500 msec (or QTcF prolongation >60 msec from Baseline)
- One or more participants in the cohort developing a liver-related finding that would stop treatment based on the liver-related AE rules outlined in [Section 10.2](#) considered as drug related
- The Investigator (or designee) and Sponsor considers that the number and/or severity of AEs, abnormal safety monitoring tests or abnormal laboratory findings justify putting the study on hold.

The Sponsor unilaterally requests it.

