#### 4.2.6 Summary and Representation of Data

Continuous data will be summarized in terms of mean, standard deviation (SD), median, minimum, maximum, and number of observations, unless otherwise stated.

Categorical data will be summarized in terms of the number of participants providing data at the relevant time point (n), frequency counts, and percentages.

The minimum and maximum will be reported to the same number of decimal places as the raw data recorded in the database. The mean and median will be reported to one more decimal place than the raw data recorded in the database. The SD will be reported to two more decimal places than the raw data recorded in the database. In general, the maximum number of decimal places reported shall be four for any summary statistics.

Percentages between 1% and 99%, inclusive, will be rounded to integers. Percentages greater than 0%, but less than 1%, will be reported as <1%, and percentages greater than 99%, but less than 100%, will be reported as >99%. If for any summary table, n is less than three then only n, minimum, and maximum should be presented, and other summary statistics will be left blank.

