- A qualitative interpretation of the ECG will be performed by the cardiologist (according to the charter referenced as "Charte\_Cardiabase\_v5.7\_2019-02-12\_AtriumV7"). This morphological interpretation will provide a codification of the abnormalities detected on the recordings according to a code list grouping the abnormalities such as Q or Qs pattern, T/U wave abnormalities, Rhythm, etc.
- More than one cardiologist from the vendor may be reviewing the ECGs in the study. However, to remove bias all ECGs of a particular participant will be reviewed by the same cardiologist. The cardiologists will also be blinded to study visits/timestamps/paroxetine dose at which the ECGs were performed. A copy should be filed in the participant's medical records. Any clinically significant finding observed on the ECG should be recorded as an AE. A copy of ECG traces (with participant-identifying details redacted) may be collected by a Sponsor appointed representative for additional cardiology review if required. Clinically significant abnormalities must be recorded on the eCRF as either medical history/current medical conditions or adverse events as appropriate.

The ECG will be evaluated by the Investigator as 'Normal', 'Abnormal, NCS' or 'Abnormal, CS'. All ECG parameters will be listed by participant including changes from baseline.

Baseline is defined in section [4.2.4](#).

If ECGs measurements are performed in triplicate, then mean of the triplicates will be presented in the listing and used for deriving baseline and changes from baseline.

Descriptive statistics for absolute values and changes from baseline will be presented by visit/ dose level and time point. Two-sided 90% confidence interval of the mean will also be calculated on changes from baseline.

Time course of mean changes from baseline with 90% confidence interval of the mean will be presented by dose level.

A summary of the number and percentage of participants per visit/dose level with ECG intervals exceeding some predefined limits (eg, >450 msec, >480 msec, >500 msec for measured values as well as, >30 msec, >60 msec for changes from baseline for QTc intervals will be displayed in a frequency table. All thresholds for the categorical analysis are presented in Section 6.4. Values meeting the thresholds for abnormality will be flagged in the individual data listings.

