**6.4 ECG Notable Criteria**

Parameter	Definition/threshold	Flag for listings
QTcF, QTcB (msec)	QTc Value >450 and $\leq$ 480 msec QTc value >480 and $\leq$ 500 msec QTc value >500 msec QTc increase > 30 and $\leq$ 60 msec QTc increase >60 msec	B H P I I+
HR (beats/min)	HR<40 beats/min HR>120 beats/min HR relative change >25%	L H I
PR (msec)	PR>220 msec PR relative change >25%	H I
QRS (msec)	QRS relative change >25% QRS>120 msec	I H

Flagging system will be used in listings to identify values meeting thresholds, also not necessarily related to clinically significant events, the flags can be interpreted as follows:

L: Low value - B: Borderline value - H: High value - P: Prolonged value

I: Noticeable increase from baseline - I+: marked increase from baseline.

QTc correspond to both QTcF and QTcB

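### On its natural reading, SAP 4.2.5 keeps unscheduled and repeat ECGs out of the QTc threshold and morphology tables, so a case that meets the study-hold criterion could be missing from them

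*SAP*

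**What the plan says.** SAP 4.2.5 states: "Repeat, retest, and unscheduled assessment will not be considered for the calculation of summary statistics and figures, unless assessment qualifies as baseline". The only exemption at the head of SAP 4.2 is "This section is not applicable to PK data", so ECG data are covered.

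SAP 4.12.5 plans "A summary of the number and percentage of participants per visit/dose level with ECG intervals exceeding some predefined limits", shown as a frequency table. A second table, also organised by visit/dose level, counts participants with a treatment-emergent morphological abnormality. SAP 6.4 gives the limits for the first table, with "QTc value >500 msec" and "QTc increase >60 msec" as the top categories. Neither section mentions unscheduled or repeat ECGs, and neither plans a worst post-baseline value.

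Unscheduled ECGs are foreseen. Protocol 8.3.3, repeated in SAP 4.12.5, says: "At visits where an ECG is not scheduled, an ECG can be performed if medically indicated". Protocol 4.1 also provides for unplanned clinic visits for adverse events during home dosing. The hold criterion in protocol 8.3.6.1, "One or more participants in the cohort experiencing QTcF interval >500 msec (or QTcF prolongation >60 msec from Baseline", is not limited to scheduled ECGs.

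**The concern.** Restricting means at nominal times to scheduled assessments is sound, because extra readings taken for cause would distort the profile. A count of participants who ever crossed a safety limit is a different quantity. There, leaving out readings can only lower the count or leave it unchanged.

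The purpose of this study is QT safety, and the two top categories of its threshold table use the same limits as its hold criterion. If the exclusion applies to that table, the study could be put on hold because of one participant's ECG while the table shows none in that category. A reader who takes the threshold table as the full account of QTc outliers would be misled, even though the value can be found elsewhere in the report.

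**Working it through.** The plan states no figure that depends on this rule, so there is none to reproduce. The check is a reading of the text, followed by a simple illustration of scale.

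**Does the rule reach the threshold table?**

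1. Scope: SAP 4.2 exempts PK data only, and SAP 4.2.5 adds one exception, for assessments that qualify as baseline. ECGs after baseline meet neither.
2. Object: the rule covers summary statistics and figures. SAP 4.2.6 says "Categorical data will be summarized in terms of the number of participants providing data at the relevant time point (n), frequency counts, and percentages", and SAP 4.12.5 calls both the threshold output and the morphology output a summary. Frequency counts therefore fall under the rule on the natural reading, although SAP 4.2.5 does not name them.
3. Restoration: SAP 4.12.5 and 6.4 contain no statement that would override the general rule.
4. Allocation: both tables are built by visit/dose level. Even if the rule did not apply, nothing says where an ECG between visits, or during the taper, would be placed.

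**How much of the dosing period has no scheduled serial ECG?** Planned dosing covers Days 1 to 31 (protocol 4.1). On-treatment serial ECGs fall on Days 7, 14 and 21 (protocol 1.3, Table 2, footnote 11). That leaves 31 − 3 = 28 dosing days, including the ten taper days (Days 22 to 31). On those days an ECG is either unscheduled or belongs to an early discontinuation visit, which the schedule of activities does provide for.

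**When is a participant lost from the table?** Only when an unscheduled or repeat ECG crosses the limit and no scheduled ECG at the same visit/dose level does. If a scheduled ECG crosses it and is then repeated, the scheduled value stays in.

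**Scale, assuming one such participant.** The inputs are 36 participants (protocol 9.5), the maximum of 40 (protocol 1.1), and the dropout scenario in SAP 4.16: 36 × 0.80 = 28.8, about 29 at 40 mg, and 36 × 0.80 × 0.75 = 21.6, about 22 at 60 mg. The proportion is 1/n. The exact one-sided 95% upper bound is 1 − 0.05^(1/n) for no cases. For one case it is the p that solves (1 − p)^n + n·p·(1 − p)^(n − 1) = 0.05.

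| n | One case | Upper bound, 0 cases | Upper bound, 1 case |
|---|---|---|---|
| 40 | 2.5% | 7.2% | 11.3% |
| 36 | 2.8% | 8.0% | 12.5% |
| 29 | 3.4% | 9.8% | 15.3% |
| 22 | 4.5% | 12.7% | 19.8% |

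These figures show what one omitted participant does to a cell. They do not say how likely that is, and the documents give no expected number of unscheduled ECGs.

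**The case against.** The best reply is that SAP 4.2.5 does not expressly cover categorical counts. SAP 4.12.5 lists descriptive statistics separately from the frequency tables, and the morphology table counts participants with at least one abnormality, which sounds like any occurrence. This stands to the extent that the omission is an inference from the text. It does not remove the need for a statement: on the more lenient reading, the tables still do not say how an ECG outside a planned visit is allocated.

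A second reply is that the event would not be lost from the report. This is correct. SAP 4.12.5 flags threshold values in the listings, and protocol 8.3.3 requires clinically significant ECG findings to be recorded as adverse events, which SAP 4.12.1 tabulates. But listings give no rate, the adverse event route depends on a judgement of significance, and the adverse event tables are by system organ class and preferred term, not by msec category.

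A third reply is that the scheduled triplicates, at 12 time points on each of Days 7, 14 and 21, already cover the assessment days for each dose, and that taper doses are lower than the Day 21 dose. This also stands. A reader might infer that the excluded ECGs are the ones most likely to be abnormal, but the documents do not show that. Unplanned visits are for adverse events or for the additional taper step, not specifically for suspected QT prolongation.

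Finally, mixing scheduled and for-cause ECGs gives participants unequal numbers of readings, which weakens comparison between dose levels. That is a reason to report the worst value over all post-baseline ECGs in its own row. It is not a reason to leave the readings out.

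**Conclusion.** The point holds in a limited form. As a stated rule, SAP 4.2.5 can bias a safety count downward, and nothing elsewhere in the plan corrects it for the threshold or morphology tables. The effect is at least one participant, 2.8% of 36, if a crossing occurs only on an unscheduled or repeat ECG; otherwise it is nil. The conclusion rests on reading frequency counts as summary statistics, which SAP 4.2.6 and 4.12.5 support without saying so outright.

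Four stronger conclusions are tempting, and the documents do not support them:

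- That the cases vanish from the report. They remain in the flagged listings and, if clinically significant, in the adverse event outputs.
- That early discontinuation and follow-up ECGs are barred. Both are in the schedule of activities, so the rule does not touch them.
- That the main conclusion is at risk. SAP 4.9.1 takes QTc for the primary analysis from the planned serial ECGs at Visits 2 to 5, and the model uses concentration-QTc pairs.
- That vital signs and laboratory tests need the same change. SAP 4.12.3 leaves clinically significant laboratory values to the adverse event summaries, and SAP 4.12.4 plans no threshold table for vital signs.

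**What to change.** State in SAP 4.2.5 or 4.12.5 that all post-baseline ECGs, including unscheduled and repeat ECGs, count in the SAP 6.4 threshold table and in the treatment-emergent morphology table. Allocate each ECG to the dose being taken at the time, or to the taper/follow-up period. Add a row for any time post-baseline, based on the worst value per participant. Keep means and figures by nominal time on scheduled ECGs only.

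No new data are needed. The cost is a small programming change and a short entry in the modification form that SAP section 1 requires for changes after finalisation. The reported outlier rates may be slightly less favourable.
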